1.5 Benefit-Risk Assessment

An evaluation of the anticipated benefits and risks as required in Article 3(2)(a) of Directive 2001/20/EC (cf. Article 6(3)(b) of Directive 2001/20/EC) has been conducted.

Riociguat (BAY 63-2521) is the first of a new class of drugs, the sGC stimulators. It is approved for 2 forms of PH (PAH and CTEPH) and is under investigation in other indications.

The cumulative worldwide exposure to riociguat (Adempas[®]) since start of marketing authorisation is estimated at 102,844 patient-months or approximately 8,570 patient-years, excluding interventional clinical studies.

At very high doses, riociguat showed maternal and fetal toxicity. The findings can be associated with the exaggerated pharmacological effects (vasodilation, blood pressure lowering) of the fetus. They are not considered prohibitive for the inclusion of women with childbearing potential if reliable contraception is provided. Riociguat should not be administered to pregnant women.

Patients with severe hepatic impairment (Child-Pugh C) have not been studied and therefore use of riociguat is contraindicated in these patients. Patients with moderate hepatic impairment (Child-Pugh B) showed a higher exposure to this medicine. Particular care should be exercised during individual dose titration.

Data in patients with severe renal impairment (creatinine clearance <30 mL/min) are limited and there are no data for patients on dialysis. Therefore, use of riociguat is not recommended in these patients. Patients with moderate renal impairment (creatinine clearance <50 - 30 mL/min) showed a higher exposure to this medicine. There is a higher risk of hypotension in patients with renal impairment, therefore particular care should be exercised during individual dose titration.

Riociguat is effective in treating patients with inoperable and persistent CTEPH after PEA, as well as patients with PAH. In patients with PAH, riociguat is effective either when administered alone or in combination with endothelin receptor antagonists (ERAs) or prostanooids. The AE profile observed in the patient populations tested was within the range expected in these chronically ill patient groups. In these severely ill patients, the overall rates of serious AEs (SAEs), AEs resulting in discontinuation of study drug and death were lower in riociguat-treated patients than in patients receiving placebo. Overall, riociguat was safe and well tolerated and did not present untoward side effects not already identified in the patient populations studied.

Patients participating in the proposed study are expected to have the same benefit of the treatment as patients previously treated with riociguat. Any positive effect on the

postoperative outcome as a result of the preoperative treatment with riociguat remains to be determined.

Also, the surgical risk depends on preoperative PVR. Riociguat can decrease the preoperative PVR and hence, can decrease the surgical risk.

Overall, the anticipated benefit-risk profile supports the investigation of riociguat in the patient population chosen for this study.

2 Study Objectives

2.1 Primary Objective

The primary objective of this study is to assess the efficacy of riociguat on preoperative PVR in patients with operable CTEPH.

2.2 Secondary Objectives

The secondary objectives of this study are the following:

- To assess the efficacy of riociguat on other preoperative pulmonary haodynamic parameters in patients with operable CTEPH
- To assess the efficacy of riociguat on postoperative pulmonary haodynamic parameters in patients with operable CTEPH
- To assess the effect of riociguat on safety and efficacy aspects during PEA in patients with operable CTEPH
- To assess the safety and tolerability of riociguat in patients with operable CTEPH

3 Investigational Plan

[figure not shown]
3.1 Study Design

This is a randomised, double-blind, placebo-controlled, multicentre, multinational, prospective study in patients with operable CTEPH prior to PEA with high preoperative PVR ($>800 \text{ dyn}\cdot\text{s}\cdot\text{cm}^{-5}$). Eligible patients will be randomly assigned to riociguat or matching placebo tid in a 1:1 ratio. A total of 88 patients are planned to randomly assign at 4 sites in North America and Europe.

A schematic of the study design is presented in Figure 3-1.

Figure 3-1

Study Schematic

Abbreviations: PEA, pulmonary endarterectomy; RHC, right heart catheterisation; V, visit

Patients will undergo a screening period of up to 89 days prior to baseline (Visit 1). Following completion of the pretreatment screening phase, eligible study patients will be randomly assigned into the study.

The study will comprise 3 study periods:

- **Screening Period (Day -89 to Day 1):** The screening period of up to 90 days will be used to assess eligibility of patients and to allow for the washout of prohibited medications. Screening visit (V0) and randomisation visit (V1) can occur on the same day.
- **Treatment Period (Day 1 [Baseline] through Day 90):** Patients will be randomly assigned on Day 1 to receive either riociguat or matching placebo tid in a 1:1 ratio for 3 months. The study drug will be initiated at 1 mg and the dosage can be increased by 0.5 mg at 2-week intervals based on tolerability (SBP) up to a maximum dose of 2.5 mg tid based on the algorithm mentioned in Section 5.2. The study drug will be initiated no later than 180 days after right heart catheterisation (RHC) (used for screening of patients) and within 90 days of planned RHC before PEA. At Visit 2, RHC will be performed per site procedures no more than 1 week prior to PEA, which will be conducted by the principal surgeon of the site. The study drug will be discontinued once PEA is performed. The last study dose will be given on the morning of PEA surgery. The patient will remain hospitalised per the investigator's discretion.
- **Follow-up Period:** A follow-up visit is planned at 6 months after PEA, at which time RHC will also be performed per study site procedures.

A telephonic call visit is planned during treatment period and at Day 186±10 during follow-up period, where treating physician or designee will call patient to ask questions related to patient's well-being and any adverse events.

Based on the quality of the RHC data and the experience of the referring site, a referred patient (a patient where the previous RHC was performed at a site other than the study site) can be enrolled in the study based on investigator's discretion. The data of haemodynamic parameters at screening will be collected from the previous RHC.

Patients who permanently discontinue study drug for any reason (ie, due to meeting the protocol-mandated safety monitoring criteria) or who withdraw from the study prematurely (prior to the end of the double-blind treatment period) will participate in the end-of-study safety follow-up visit.

Efficacy and safety assessments will be performed throughout the study, as presented in the schedule of events (Table 12-1). The primary efficacy measure is the reduction in PVR.

Additional efficacy measures include cardiac index, mean right atrial pressure (mRAP), mPAP, pulmonary artery wedge pressure (PAWP), number and cause of deaths during the study, PH-related hospitalisation, need for PAH-targeted and other medications, change in WHO functional class for PAH, perioperative findings that include circulatory arrest time and surgery-related complications, surgical evaluation of specimen, withdrawal during the treatment phase, NT-proBNP concentration, length of hospital and intensive care unit (ICU) stay, and time on mechanical ventilation.

Safety assessments include monitoring of AEs, vital sign measurements, electrocardiogram (ECG) measurements, physical examinations, clinical laboratory examinations, and pregnancy testing.

The end of the study is defined as when the last patient completes the last visit of the study ie, 6-month follow-up visit (Visit 4).

An unblinded, independent data safety monitoring board will periodically review safety data and other study information during the conduct of the study.

3.1.1 Rationale of Study Design

Riociguat, an sGC stimulator, is the first approved treatment of persistent/recurrent CTEPH after surgical treatment or inoperable CTEPH to improve exercise capacity. Riociguat is also authorised for the indication of PAH. The primary endpoint in the pivotal study, CHEST-1, was change from baseline to Week 16 in the 6-minute walking distance. An increase of 39 meter was observed in the riociguat group compared to a decrease of 6 meter in the placebo group. Pulmonary vascular resistance decreased by $226 \text{ dyn}\cdot\text{s}\cdot\text{cm}^{-5}$ in patients treated with riociguat compared to an increase of $23 \text{ dyn}\cdot\text{s}\cdot\text{cm}^{-5}$ in the placebo group. Significant improvements were also observed in other haemodynamic variables including pulmonary artery pressure and cardiac output (Ghofrani et al 2013). Improving pulmonary haemodynamics before surgery could potentially reduce the morbidity and mortality associated with PEA. Two case series examined a total of 21 patients treated with intravenous epoprostenol prior to PEA. An improvement in pre-PEA haemodynamics, but no change in post-PEA haemodynamics was observed compared to controls, possibly due to controls having less severe disease (Bresser et al 2004; Nagaya et al 2003). A prospective study with inhaled iloprost in 10 patients demonstrated a worsening of haemodynamics during surgery but an improvement was seen in the ICU with continued treatment with inhaled iloprost compared to inhaled saline (Kramm et al 2003). In a randomised study, pretreatment with bosentan for 6 months demonstrated a reduction in

pre-PEA, PVR, mPAP, and mRAP but no difference in post-PEA haemodynamics compared to controls (Reesink et al 2010). To date there is no convincing evidence that preoperative treatment of technically operable CTEPH with ERAs, PDE5 inhibitors, or prostanooids is beneficial.

This study will investigate if pre-PEA treatment with riociguat in technically operable CTEPH can improve preoperative pulmonary haemodynamics and key clinical outcomes after PEA. The current study is a randomised, double-blind, placebo-controlled, multicentre, prospective study of a 3-month treatment period followed by a 6-month safety follow-up period in patients with operable CTEPH with high preoperative PVR.

This study requires blinded comparison of active treatment with placebo treatment. As the use of a placebo control offers substantial protections against bias, a double-blind, placebo-controlled clinical trial is the most rigorous test of treatment efficacy. Use of placebo provides an opportunity to obtain information regarding the full treatment effect size for riociguat and also best enables the determination of whether AEs are due to treatment or to the disease condition. For these reasons, double-blind, placebo-controlled trials are almost always mandated for regulatory approval of an investigational drug for a specific disease indication.

Furthermore, it should be noted that placebo (or active drug) is used as premedication in addition to planned PEA. Placebo and active treatment will be compared in an "add-on" approach to patients scheduled to receive surgical treatment of CTEPH. Therefore, the trial does not include additional risks associated with the treatment with placebo. The patients will be fully informed of the risks involved in assignment to the placebo group.

4 Patient Selection and Withdrawal Criteria

4.1 Selection of Study Population

Approximately 88 patients will be enrolled at 4 high-volume experienced sites in North America and Europe. Patients will be assigned to study drug only if they meet all of the inclusion criteria and none of the exclusion criteria.

Deviations from the inclusion and exclusion criteria are not allowed because they can potentially jeopardise the scientific integrity of the study, regulatory acceptability, or patient safety. Therefore, adherence to the criteria as specified in the protocol is essential.

4.1.1 Inclusion Criteria

Each patient must meet all of the following criteria to be enrolled in this study:

1. Is a male or nonpregnant and nonlactating female patient aged from 18 to 80 years, both inclusive
2. Is diagnosed with operable CTEPH and anticipating symptomatic and/or prognostic benefit from PEA
3. Has PVR >800 dyn·s·cm⁻⁵
4. Has undergone RHC not more than 180 days before Visit 1
5. Has been treated with anticoagulants for at least 90 days before Visit 1
6. Has ability to swallow oral medication
7. Has ability and willingness to participate and access to the health facility
8. Is capable of understanding the written informed consent and provides signed and witnessed written informed consent
9. Female patient must be either surgically sterile, postmenopausal (no menses for the previous 12 months), or must be practicing an effective method of birth control as determined by the investigator (eg, oral contraceptives, double barrier methods, hormonal injectable or implanted contraceptives, tubal ligation, or male partner with vasectomy or complete abstinence)

4.1.2 Exclusion Criteria

Patients meeting any of the following criteria will be excluded from the study:

1. Has unstable disease in need of urgent PEA surgery as determined by the treating physician
2. Has known hypersensitivity, allergic, or adverse reactions to riociguat or any of the excipients comprising riociguat tablets
3. Has known active hepatitis A immunoglobulin M, hepatitis B surface antigen, or hepatitis C antibody
4. Is human immunodeficiency virus positive
5. Has pulmonary veno-occlusive disease
6. Has symptomatic hypotension
7. Has symptomatic carotid disease
8. Has significant coronary atherosclerotic disease in need of intervention
9. Has severe left heart disease in need of intervention
10. Has redo sternotomy
11. Has received any background therapy for PAH in the preceding 30 days before Visit 1 including ERAs, PDE5 inhibitors, or prostanooids
12. Is receiving nitrates, NO donors (eg, amyl nitrite), ERAs, prostanooids, specific PDE5 inhibitors, nonspecific phosphodiesterase inhibitors (eg, dipyridamole, theophylline)
13. Is receiving strong cytochrome P450 and P-glycoprotein/breast cancer resistance protein inhibitors
14. Is receiving strong cytochrome P450 3A inducers
15. Has creatinine clearance <15 mL/min or is on any form of dialysis
16. Has severe hepatic impairment classified as Child-Pugh B or C

17. Has received an investigational drug within the past 4 weeks before Visit 1
18. Is a lactating or pregnant (as demonstrated by a serum or urine dipstick pregnancy test) woman, or not willing to take measures not to become pregnant during the 3-month treatment study period and 1 month after the last dose of study drug administered
19. Has smoked or used tobacco in any form, including snuff or chewing within 3 months prior to Visit 1
20. Has idiopathic interstitial pneumonitis

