5.2 Treatments Administered

Patients will initiate the treatment with either riociguat or matching placebo tablets orally tid for 3 months. The study drug will be initiated no later than 180 days after RHC (used for screening of patients) and within 90 days of planned RHC before PEA. Right heart catheterisation will be performed within 3 months of the initiation of treatment per site procedures no more than 1 week prior to PEA. The study drug will be initiated at 1 mg and the dosage can be increased by 0.5 mg at 2-week intervals based on tolerability (SBP) up to a maximum dose of 2.5 mg tid. The individual study drug dose of the next titration step will be determined every 2 weeks at home according to the peripheral SBP measured at trough before intake of the morning dose under consideration of the following algorithm:

- If trough SBP \geq 95 mmHg, increase dose (+0.5 mg tid)
- If trough SBP $<$ 95 mmHg without symptoms of hypotension, maintain dose
- If any SBP $<$ 95 mmHg with clinical symptoms of hypotension such as dizziness or presyncope, stop study drug; restart after 24 hours with reduced dose (-0.5 mg tid)

The BP measuring device will be supplied along with study drug to each patient to monitor BP at home. If the dose is interrupted for 3 or more days, restart the dose with 1 mg tid and follow the up-titration algorithm. The up titration will be monitored by study staff contacting the patient by telephone at home.

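### Exclusion criterion 15 admits patients with creatinine clearance of 15 to <30 mL/min, for whom Protocol section 1.5 does not recommend riociguat; raise the cut-off to <30 mL/min

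*Protocol*

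**What the plan says.** Protocol section 4.1.2, criterion 15, excludes a patient who "Has creatinine clearance <15 mL/min or is on any form of dialysis". The synopsis has the same criterion. Section 4.2 repeats it among the laboratory-based exclusions and requires confirmation at Visit 1 in every patient.

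The benefit-risk assessment in section 1.5 uses a different threshold. It states: "Data in patients with severe renal impairment (creatinine clearance <30 mL/min) are limited and there are no data for patients on dialysis". The next sentence draws the consequence: "Therefore, use of riociguat is not recommended in these patients". It then reports higher exposure in moderate impairment (30 to <50 mL/min) and adds: "There is a higher risk of hypotension in patients with renal impairment, therefore particular care should be exercised during individual dose titration".

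Section 5.2 gives one dosing rule for all patients. Treatment starts at 1 mg tid, and "the dosage can be increased by 0.5 mg at 2-week intervals based on tolerability (SBP) up to a maximum dose of 2.5 mg tid". Each step depends on trough systolic pressure measured at home, with 95 mmHg as the threshold.

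For the liver, section 1.5 states a contraindication for Child-Pugh C only. For the next grade it says "Patients with moderate hepatic impairment (Child-Pugh B) showed a higher exposure to this medicine" and asks for care during titration. Criterion 16 nevertheless excludes both grades: "Has severe hepatic impairment classified as Child-Pugh B or C".

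**The concern.** Two thresholds in one protocol disagree, and the gap between them contains eligible patients. At 15 to <30 mL/min a patient passes criterion 15 but belongs to the group for which section 1.5 says the drug should not be recommended.

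What is at stake is the safety of those patients. Section 1.5 names the hazard (hypotension) and the response (extra care in titration), but section 5.2 does not turn that response into anything specific to renal function. The plan also gains nothing from enrolling this band. If the aim were to add data where data are limited, a renal analysis would be expected. The safety subgroups in SAP section 4.4 are defined only by direct oral anticoagulants, vitamin K antagonists and β-blockers.

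**Working it through.** The plan states no figure to reproduce, so the check is a comparison of texts plus simple dose arithmetic.

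**1. The two thresholds**

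| Source | Creatinine clearance | Consequence |
|---|---|---|
| Section 1.5 | <30 mL/min | riociguat not recommended, because data are limited |
| Section 1.5 | dialysis | riociguat not recommended, because there are no data |
| Criterion 15 (synopsis, 4.1.2, 4.2) | <15 mL/min, or dialysis | excluded |

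Band that is eligible but not recommended: 15 to <30 mL/min.

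**2. Is a reason given?** Neither the protocol, the amendment log nor the SAP explains the 15 mL/min cut-off. The nearest text is the closing sentence of section 1.5, that "the anticipated benefit-risk profile supports the investigation of riociguat in the patient population chosen for this study". That is a general conclusion and does not mention this band. The same section expects trial patients to benefit as previously treated patients did, an expectation that is weakest where the protocol itself says data are limited.

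**3. Kidney against liver**

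| Group | Wording in section 1.5 | Eligibility |
|---|---|---|
| Child-Pugh C | contraindicated | excluded |
| Child-Pugh B | higher exposure, titrate with care | excluded |
| Creatinine clearance 15 to <30 mL/min | not recommended | admitted |

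The weaker warning leads to exclusion and the stronger one does not.

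**4. Dose that a patient in the band can reach.** Inputs are from section 5.2: start 1 mg tid, step 0.5 mg tid, interval 2 weeks, maximum 2.5 mg tid.

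- Steps to maximum: (2.5 − 1.0) / 0.5 = 3
- Time to maximum: 3 × 2 weeks = 6 weeks
- Starting daily dose: 1.0 × 3 = 3 mg/day
- Maximum daily dose: 2.5 × 3 = 7.5 mg/day

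This is the fastest path, taken when trough pressure is at or above 95 mmHg at every step. It is the same for a patient with normal renal function. Between Visit 1 (Day 1) and Visit 2 (about Day 90) the schedule of events lists no laboratory test, so all of the titration falls between two scheduled renal measurements.

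**5. How many patients?** The documents give no distribution of renal function in this population, so the number of the 88 who would fall in the band cannot be computed. Allocation is 1:1, so about half of any such patients would receive riociguat.

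**The case against.** The strongest reply is that a statement that a drug is not recommended is not an exclusion rule. Section 1.5 distinguishes a contraindication from a lack of recommendation, and limited data from no data. Criterion 15 does exclude dialysis patients, the no-data group. A monitored Phase 2 trial may enrol patients on whom data are sparse. Section 4.1.2 gives no reason for any of its 20 criteria, and two amendments touched the eligibility text without moving this cut-off, so it may be deliberate.

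There are also real safeguards: exclusion of symptomatic hypotension, pressure-gated titration, a home device with telephone monitoring, hypotension as an adverse event of special interest, investigator-led withdrawal, central-laboratory creatinine clearance at Visits 1 and 2, and DSMB review. The number affected may be nil. A hepatic criterion stricter than section 1.5 does not by itself make the renal one wrong.

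Much of this stands. Eligibility is unambiguous, no contraindication is breached, and the safeguards reduce the hypotension risk. But they apply to every patient and do not answer the reason section 1.5 actually gives, which is limited data. The hepatic comparison is not proof of error; it shows only that the protocol's warnings were not carried into eligibility in a consistent way. An unknown and probably small number weakens the urgency, but it equally means that the change would cost little recruitment.

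**Conclusion.** The concern holds. Followed as written, the protocol would randomise patients at 15 to <30 mL/min to a drug that its own benefit-risk section does not recommend for them. It names a higher hypotension risk, has no renal provision in the titration rule, gives no reason and plans no renal analysis.

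The size is limited. The number of patients cannot be computed from the documents, and the dose arithmetic describes exposure on the fastest path, not measured harm. There is no effect on the primary analysis or on the sample size, which section 7.5 bases on feasibility. The conclusion rests only on the protocol's own text. It assumes that no justification exists in a document not available here, such as the investigator's brochure. The change should be made, because it removes an avoidable risk cheaply; the plan is not invalid without it.

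**What to change.** In the synopsis, section 4.1.2 and section 4.2, change the cut-off in criterion 15 from <15 to <30 mL/min and keep the dialysis clause. The Visit 1 laboratory confirmation already required in section 4.2 then checks the new limit. The SAP does not restate the threshold, so it needs no change there.

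Patients in the band who were randomised before the amendment continue under section 5.2 and stay in the ITT and safety sets. For the per-protocol set they are judged against the criteria in force when they were randomised. SAP section 4.3.3 has no such rule, so add one sentence to it.

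The cost is one number in three places, that SAP sentence, and the ethics and regulatory approval that any amendment needs under section 10.2.1. The trade-off is a slightly narrower population. If the sponsor chose 15 mL/min on purpose, section 1.5 should say why; that would explain the inconsistency but would not reduce the risk to these patients.
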